The Effect of Lumbar CSF drainage on the Neurologic Outcome Improvement

in OHCA underwent TTM

1. Introduction

Global cerebral ischaemic-reperfusion brain injury following cardiac arrest (CA) can lead to intracranial hypertension and, occasionally, acute brain swelling [1,2]. Even small increases in brain volume due to oedema can result in harmful increases in intracranial pressure due to the brain's rigid encasement. The previous studies demonstrated a higher intracranial pressure (ICP) was strongly associated with and seemed predictive of a poor outcome, and higher ICP following global cerebral ischaemia immediately after ROSC, and severe blood-brain barrier (BBB) disruption began at 24 h after ROSC in the poor neurologic outcome group treated with target temperature management (TTM) [3, 4].

Several therapeutic approaches have been established for the treatment of increased ICP in traumatic brain injury, including TTM, elevation of the head, sedation, volume resuscitation, maintenance of adequate arterial oxygenation, cerebrospinal fluid drainage via a ventriculostomy, moderate hyperventilation, and mannitol administration [5]. However, despite these various therapies, a considerable number of patients remain nonresponsive to aggressive management strategies. During the last decades, controlled lumbar cerebrospinal fluid (CSF) drainage has been considered to be contraindicated in the setting of increased ICP because of the possibility of transtentorial or tonsillar herniation [6–8]. In contrast, a recent report on the use of lumbar CSF drainage to treat refractory increased ICP suggested that this controversial therapeutic strategy might be efficient and a valuable treatment when applied to carefully selected patients had discernible basal cisterns and controlled release of CSF under monitoring of ICP and vital signs [9, 10]. Plus, much of the CSF volume is present in the subarachnoid spaces and cisterns around the brain. This CSF is not accessible for drainage by ventriculostomies but is accessible by lumbar drainage [11].

However, to the best of our knowledge, there is no study on the effect of lumbar CSF drainage to improve neurologic outcome in CA patients treated with TTM. We aimed to evaluate the effect of lumbar CSF drainage on neurologic outcome in post-CA patients treated with TTM.

2. Methods

This study was approved by the Institutional Review Board of the Chungnam National University Medical Centre (CNUH IRB 2019-07-033-003). We obtained approval and consent from the next of kin before enrolment.

2.1. Study design and patients

This was a prospective single-centre study conducted from November 2019 to October 2021 on patients who had been treated with TTM following CA. The primary endpoint was to evaluate the effect of the lumbar CSF drainage on attenuation of brain swelling and improvement of the neurologic outcome in post-CA patients treated with TTM. The data were collected from the electrical medical record. We named the patients were treated with our standard protocol as the non-lumbar CSF drainage group, whereas the patients treated with the protocol and the lumbar CSF drainage were called as the lumbar CSF drainage group. The neurologic status of the patients was obtained on the 6-month follow-up after return of spontaneous circulation (ROSC). Neurological outcome was assessed using the Glasgow-Pittsburgh cerebral performance categories (CPC) scale. The good outcome group was defined as a CPC 1 or 2, and the poor outcome group as a CPC between 3 and 5. Resuscitated cardiac arrest patients whose Glasgow coma scale (GCS) was 8 or less after the return of spontaneous circulation (ROSC), and who underwent TTM were included in the study. The exclusion criteria for this study were as follows: (1) \leq 18 y of age, (2) traumatic CA or interrupted TTM (due to haemodynamic instability), (3) not eligible for TTM (i.e., intracranial haemorrhage, active bleeding, known terminal illness, or poor pre-arrest neurological status), (4) ineligible for LP (i.e., brain computed tomography showed severe cerebral oedema, obliteration of the basal cisterns, occult intracranial mass lesion, or coagulopathy: platelet count $< 40 \times 10^3$ /mL or international normalized ratio (INR) > 1.5),¹² (5) on extracorporeal membrane oxygenation, (6) unable to consent to LP, and (7) refusal of further treatment by the next of kin.

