2.3. Data collection

The following data were collected from the database: age, sex, presence of a witness at the time of the collapse, bystander cardiopulmonary resuscitation (CPR), first monitored rhythm, aetiology of cardiac arrest, time from collapse to CPR (no flow time), time from CPR to ROSC (low flow time), sequential organ failure assessment (SOF) score, ICP measured on immediate after ROSC, time from ROSC to inserting a lumbar drainage catheter placed through the lumbar vertebral interspace into the subarachnoid space (ICP time), , and CPC at 6 months after ROSC.

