2.5. MRI protocol and analysis

Our hospital has a standardised magnetic resonance imaging (MRI) protocol for non-traumatic OHCAs. MRI imaging includes diffusion weighted image (DWI), and apparent diffusion coefficient (ADC) map. The MRI was obtained between 72–96 h after ROSC. Forty contiguous DWI sections per patient were acquired using a 3T scanner (Achieva 3 T; Philips Medical System, The Netherlands). The standard of b=1000 s/mm² was used for all DWIs. ADC maps were created from the mono-exponential calculation of DWI with a commercial software and workstation system (Leonardo MR Workplace; Siemens Medical Solutions, Erlangen, Germany). For quantitative analysis of ADC to evaluate the effect of lumbar CSF drainage on attenuation of brain swelling, images were processed and analysed using software (FMRIB Software Library, Release 5.0 (c) 2012, The University of Oxford) that can extract brain tissue by eliminating cranium, optic structure, and extra-cranial soft tissues. Images were retrieved in Digital Imaging and Communications in Medicine format from picture archiving and communication system servers at the hospital and were converted to NITFI format using MRIcron (http://www.nitrc.org/projects/mricron). ADC thresholds ranged from 0 to 1590 X 10⁻⁶ mm²/s to exclude artefacts or pure CSF [16]. The percentage of voxels (PV) meant number of voxels below different ADC thresholds was divided by total number of voxel.

The % voxels of ADC values (PV)

$$PV = \frac{Voxel \text{ numbers of ADC value}}{Voxel \text{ numbers of ADC value}} \frac{ADC \text{ threshold}}{0}$$

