2.6. Sample size

A previous study reported ICP on 24 h after ROSC was 13.22 ± 3.99 mmHg in good outcome and 18.57 ± 5.61 mmHg in poor outcome [17], 62 patients were needed to achieve the power of 0.99 at a significance level of 0.05 (two-sided test).

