2.7. Statistical analysis

NCT number: not yet assigned

We reported continuous variables as median with interquartile range or as mean and standard deviation depending on the normal distribution. Categorical variables were reported as frequencies and percentages. We performed the propensity score matching with age, sex, presence of a witness at the time of the collapse, bystander CPR, first monitored rhythm, causes of CA, no flow time, low flow time, sequential organ failure assessment (SOFA) score, and ICP on immediate after ROSC between both groups. Comparisons between the two groups were made using the chi-square test, Fisher's exact test, the Mann-Whitney U test, or two-tailed *t*-test. Multivariate logistic regression models were built to identify the effect of the lumbar CSF drainage on the neurologic outcome at 6 months after ROSC. The estimated odds ratio was considered to assess risk. All statistical analyses were performed using the PASW/SPSSTM software, version 18 (IBM Inc., Chicago, USA). Results were considered significant at P < 0.05.

Conflict of interest statement: The authors have no conflict of interest to report

Acknowledgements: This work was supported by the National Research Foundation Korea (NRF) grant funded by the Korea government (MSIT) (No. 2019R1F1A1041024).

References

2. Polderman KH. Mechanisms of action, physiological effects, and complications of hypothermia. Crit Care Med 2009;37:S186–202.

6. Cushing H. Some aspects of the pathological physiology of intracranial tumors. *Boston Med Surg J* 1909; 141:71–80.

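### The primary endpoint joins brain swelling and neurologic outcome with no rule for success, and no ADC threshold is named for the swelling part, so what counts as a positive primary result is undefined.

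*Combined protocol and SAP*

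**What the plan says.** Section 2.1 puts two outcomes into one primary endpoint: "The primary endpoint was to evaluate the effect of the lumbar CSF drainage on attenuation of brain swelling and improvement of the neurologic outcome". The neurologic part is CPC at 6 months, split into good (1 or 2) and poor (3 to 5). The swelling part is taken up in section 2.5, which introduces the MRI measure with "For quantitative analysis of ADC to evaluate the effect of lumbar CSF drainage on attenuation of brain swelling" and defines it so: "The percentage of voxels (PV) meant number of voxels below different ADC thresholds was divided by total number of voxel". The range of 0 to 1590 given there removes artefacts and pure CSF; it is not an endpoint cut-off.

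Section 2.7 sets one significance limit, P < 0.05, for all results. It lists general two-group tests and a logistic regression for the 6-month neurologic outcome. No section gives a success rule, a testing order, a split of alpha or an adjustment for multiplicity.

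Other text leans towards the neurologic outcome. The title names it alone, and the Introduction ends: "We aimed to evaluate the effect of lumbar CSF drainage on neurologic outcome in post-CA patients treated with TTM". The regression in 2.7 also concerns it alone. Yet no section makes swelling secondary. Section 2.6 does not settle the matter, because its calculation rests on ICP at 24 h in good-outcome versus poor-outcome patients, which is neither component.

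**The concern.** The two components are measured by different instruments at different times: MRI at 72-96 h and CPC at 6 months. They can disagree. As the plan stands, a significant PV difference at one threshold, with no difference in CPC, could be reported as meeting the primary endpoint, although the stated aim is neurologic outcome. A reader would not know how many thresholds had been examined, or whether the rule for success was chosen before or after the results were seen.

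**Working it through.** **1. The plan's own figure.** Inputs from section 2.6: means 13.22 and 18.57 mmHg, SDs 3.99 and 5.61, two-sided 0.05, power 0.99. A 1:1 split is assumed, because none is stated.
- Difference = 18.57 − 13.22 = 5.35. Pooled SD = √[(3.99² + 5.61²)/2] = 4.87. Standardised difference = 5.35/4.87 = 1.10.
- n per group = 2(1.960 + 2.326)²/1.099² = 30.4, rounded up to 31, so 62 in total.

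This reproduces "62 patients were needed to achieve the power of 0.99 at a significance level of 0.05 (two-sided test". The arithmetic is sound, and the fault lies in the endpoint and testing rule. The figure of 31 per group is used in step 5.

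**2. Either outcome suffices.** Assume one test per outcome, each with a true two-sided level of 0.05, and no real effect on either. Independent tests give
- either direction: 1 − 0.95² = 0.0975, against 0.05 for one test;
- benefit direction: 1 − 0.975² = 0.0494, against 0.025 for one test.

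For correlated tests, take the bivariate normal with critical value 1.96. The documents give no correlation, so a range is shown. Positive values mean that less swelling goes with better CPC.

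| Correlation | Either direction | Benefit direction |
|---|---|---|
| 0 | 9.75% | 4.9% |
| 0.5 | 9.1% | 4.5% |
| 0.7 | 8.3% | 4.2% |
| 0.9 | 7.0% | 3.5% |

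9.75% is the maximum for jointly normal two-sided tests; with no assumption about dependence the bound is 10% (0.05 + 0.05). The benefit-direction 4.9% is the maximum for correlations of zero or above; the bound without that assumption is 5% (0.025 + 0.025).

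**3. Both outcomes required.** On the same benefit-direction scale, with one swelling test and neither effect real, the chance of false success is 0.025² = 0.06% at correlation 0, 0.5% at 0.5 and 1.5% at 0.9. If CPC has no true effect, it cannot exceed 2.5%, because CPC itself must be significant. Two outcomes therefore add no inflation.

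**4. Several thresholds.** Suppose swelling may be claimed at any significant threshold. With k thresholds, the chance of at least one false significant PV result exceeds 5% unless the tests are perfectly correlated, and it reaches 1 − 0.95^k if they are independent. PV at neighbouring thresholds is probably strongly correlated, so the truth would lie between these. Neither k nor the correlation is in the documents, so the size is unknown. This problem remains when both outcomes are required: if drainage truly improves CPC, the swelling half is then the only guard, and it is not held at its level.

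**5. What an ordered rule would cost.** Exact power of the unadjusted chi-square test for CPC, 31 per group, benefit direction, with assumed good-outcome rates without drainage of 30% and 50%:

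| Difference | From 30% | From 50% |
|---|---|---|
| 10 points | 12.7% | 12.9% |
| 20 points | 37.1% | 37.1% |
| 30 points | 68.9% | 71.4% |

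**The case against.** The strongest reply is that 2.1 says *and*. Read literally, both outcomes must succeed, and step 3 shows that the error is then not raised by having two of them. This stands as a possible reading, and it is why the 9.75% is conditional. A reader might infer that the study simply runs at 9.75%. The documents do not support that: they never say that either outcome is enough, and the figure counts harmful as well as beneficial differences, whereas the endpoint speaks of attenuation and improvement. But nor do they say that both are required, and that reading leaves the threshold open.

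A second reply is that CPC is plainly the main outcome. The title, the aim and the regression support this, and it is a good reason to choose CPC in the repair. It does not change 2.1, which places swelling in the primary endpoint. One might add that the list in 2.3 ends with "and CPC at 6 months after ROSC" and names no MRI measure. That inference is unsafe, because an empty item stands just before CPC and text may have been lost there.

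Two further readings go too far. One is that the plan has no test for PV. PV is not named in 2.7, but it is a continuous percentage and the two-group tests listed there would cover it. The other is to attach a firm figure to the choice of threshold: nothing in the documents gives the number of thresholds or says that any significant one would be claimed.

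Finally, the study may be over: "This was a prospective single-centre study conducted from November 2019 to October 2021". That limits what a new rule can achieve, but not the value of declaring one.

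**Conclusion.** The point holds as a gap in the definition of primary success. Two outcomes share the primary endpoint with no rule for combining them, one has an unstated number of thresholds, and every result is judged at 0.05. If either outcome may be claimed, the false-positive chance for two tests is nearly doubled: 9.75% instead of 5% in either direction, or 4.9% instead of 2.5% for benefit, falling to 7.0% and 3.5% at correlation 0.9. If both are required, that inflation vanishes and only the open threshold remains, with a size that cannot be computed.

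These figures assume that each test has a true 5% level. The study is not described as randomised, and "We performed the propensity score matching with age, sex, presence of a witness at the time of the collapse" (among other covariates) shows that confounding is expected. Confounding could break the nominal level whatever multiplicity rule is adopted. The change should be made, but the documents do not show that a false claim was or would be made.

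**What to change.** In 2.1 and 2.7, state: *The primary endpoint is CPC 1-2 at 6 months, tested at two-sided 0.05. Brain swelling is the key secondary endpoint, tested at two-sided 0.05 only if the primary is significant.* This agrees with the title, the aim and the regression.

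If the sponsor wants both to stay primary, state one of these instead:
- both must be significant at two-sided 0.05; or
- each is tested at 0.025, which gives 1 − 0.975² = 4.94% if independent and never more than 5%.

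In 2.5, name one ADC threshold for the swelling comparison, chosen by the sponsor and fixed before outcome data are linked. Report PV at other thresholds descriptively, without significance claims. In 2.7, name the test for PV.

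The cost is wording only; no new data are needed. Under the ordered rule, a swelling-only result can no longer be claimed as primary success, and swelling will often go formally untested. With 31 per group (assumed), CPC is significant for benefit about 13% of the time for a 10-point difference and 37% for a 20-point difference, and less often if matching drops patients or Fisher's exact test is used. Requiring both cannot succeed more often than CPC alone, and the split lowers the power of each test.

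If analysis has begun, declare the rule and the threshold as post hoc; they then carry less weight. None of the options removes confounding.

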2.2. TTM protocol

NCT number: not yet assigned

We have applied our protocol and TTM using cooling devices (Arctic Sun [®] Energy Transfer Pads TM, Medivance Corp., Louisville, USA) for patients who had sustained ROSC since March, 2016. Our protocol was as follows; (1)the target temperature of 33°C was maintained for 24 h with rewarming to 37.0°C at the rate of 0.25°C/h, (2) was monitored using an oesophageal and bladder temperature probe, (3) sedatives and analgesics were used during TTM and patients received standard care according to the protocol described in a previous study included deep sedation, (4) mild hyperventilation (PaCO2 35~45 mmHg), (5) mean arterial pressure (MAP) was maintained between 80 and 110 mmHg via vasoactive support with norepinephrine and, if needed, plasma volume expansion with crystalloids, (6) adequate arterial oxygenation between 150 and 250 mmHg, (7) patients were placed in supine position with 30° head-up tilt, (8) anti-epileptic medications were administered as soon as a seizure was suspected either clinically or through EEG [13].

2.3. Data collection

The following data were collected from the database: age, sex, presence of a witness at the time of the collapse, bystander cardiopulmonary resuscitation (CPR), first monitored rhythm, aetiology of cardiac arrest, time from collapse to CPR (no flow time), time from CPR to ROSC (low flow time), sequential organ failure assessment (SOF) score, ICP measured on immediate after ROSC, time from ROSC to inserting a lumbar drainage catheter placed through the lumbar vertebral interspace into the subarachnoid space (ICP time), , and CPC at 6 months after ROSC.

2.4. ICP control via lumbar CSF drainage

We have performed the lumbar CSF drainage on the level of the lumbar spine between L3 and L4 with the patient lying in the lateral decubitus position with hips and knees flexed. A lumbar drainage catheter was inserted using a HermeticTM lumbar accessory kit (Integra Neurosciences, Plainsboro, NJ, USA) in the patients. ICP monitoring via lumbar drainage catheter was practiced using the *LiquoGuard*[®] (Möller Medical GmbH & Co KG, Fulda, Germany). ICP control strategies was initiated when ICP exceeded 15 mmHg in the absence of noxious stimuli at the rate of 10~20 ml/h via a lumbar drainage catheter

until ICP was less than 15 mmHg [14, 15].

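### CSF release depends on ICP exceeding 15 mmHg, the plan does not say whether catheterised but undrained patients count as drained, and the 0.99 power does not apply to the drainage comparison

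*Combined protocol and SAP*

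**What the plan says.** - **Group (2.1).** The treated group is defined by one clause: "the patients treated with the protocol and the lumbar CSF drainage were called as the lumbar CSF drainage group". Eligibility rests on coma after ROSC and on receiving TTM. No minimum ICP is set, and severe oedema or obliterated basal cisterns on CT excludes a patient.
- **Intervention (2.4).** A lumbar catheter is placed and ICP is monitored through it. Release is conditional: "ICP control strategies was initiated when ICP exceeded 15 mmHg in the absence of noxious stimuli", and it continues "until ICP was less than 15 mmHg". The catheter therefore comes before any decision to drain.
- **Sample size (2.6).** The basis is an earlier study's 24 h ICP: "13.22 ± 3.99 mmHg in good outcome and 18.57 ± 5.61 mmHg in poor outcome [17], 62 patients were needed to achieve the power of 0.99".
- **Analysis (2.7).** "Multivariate logistic regression models were built to identify the effect of the lumbar CSF drainage on the neurologic outcome at 6 months after ROSC". ICP immediately after ROSC is one of ten variables in the propensity score. There is no analysis set, no ICP stratum and no group-by-ICP term. The plan does not say how a catheterised patient with no CSF released is classified.

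**The concern.** A patient whose ICP stays at or below 15 mmHg has a catheter but no CSF released. If such patients are analysed as drained, the odds ratio for CPC and the difference in PV average any effect in drained patients with little or no effect in the rest. A real benefit could be missed, and a null result could mean either that drainage does not help or that many patients were not drained.

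If such patients are instead left out or counted as non-drainage, the groups are selected by ICP, which 2.6 itself shows to differ by outcome. Either way, the reader needs to know the rule.

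The 0.99 in 2.6 carries no condition about how many patients are drained and reads as the power of the study's main comparison.

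**Working it through.** **Inputs.** From 2.6: good outcome, mean 13.22, SD 3.99; poor outcome, mean 18.57, SD 5.61 (mmHg at 24 h); N = 62; power 0.99; two-sided 0.05. From 2.4: trigger 15 mmHg. Assumed, because not stated: equal groups (31 v 31), normal ICP, the share of good outcomes, and that the earlier study's values represent ICP without drainage.

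**1. The plan's own figure.**
- Difference = 18.57 − 13.22 = 5.35.
- Pooled SD = √((3.99² + 5.61²)/2) = 4.87, so d = 5.35/4.87 = 1.10.
- n per group = 2 × ((1.960 + 2.326)/1.099)² = 30.4, rounded up to 31, total 62. The plan's figure is reproduced.
- Power at 31 v 31 is 0.991 (normal) or 0.989 (t-test).

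The arithmetic is right for its inputs. But the two means compared belong to good- and poor-outcome patients, not to drained and undrained patients.

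**2. Share above the trigger at 24 h.**
- Good outcome: 1 − Φ((15 − 13.22)/3.99) = 1 − Φ(0.446) = 0.328.
- Poor outcome: 1 − Φ((15 − 18.57)/5.61) = 1 − Φ(−0.636) = 0.738.
- Even split: (0.328 + 0.738)/2 = 0.533. With 60% good outcomes it is 0.492; with 30% it is 0.615.

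**3. What the drain-to-15 rule could do to mean 24 h ICP.** Suppose every value above 15 is brought down to 15 and no other value changes. The mean fall is (m − 15) × P(ICP > 15) + s × φ((15 − m)/s), where φ is the standard normal density.
- Good outcome: (−1.78 × 0.328) + (3.99 × 0.361) = 0.86 mmHg.
- Poor outcome: (3.57 × 0.738) + (5.61 × 0.326) = 4.46 mmHg.
- Even split: (0.86 + 4.46)/2 = 2.66 mmHg.

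Holding the SD at 4.87, t-test power at 31 v 31 is about 0.56 for 2.66 mmHg (d = 0.55) and about 0.94 for 4.46 mmHg (d = 0.92). Neither reaches the 5.35 mmHg used for sizing.

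**4. Proportional loss, as illustration only.** If a share f of the group is ever drained and the rest have no effect, the standardised difference is f × 1.10. At 31 v 31 (t-test):

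| Share ever drained | d × f | Power |
|---|---|---|
| 53% | 0.58 | 0.62 |
| 74% | 0.81 | 0.88 |
| 90% | 0.99 | 0.97 |
| 100% | 1.10 | 0.99 |

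These rows show how quickly power falls as f falls. They are not the trial's power for CPC or PV, because d = 1.10 is not a drainage effect.

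**5. Would restricting to patients above 15 mmHg help?** At 53%, the stratum is about 16 v 16 (31 × 0.53), with power 0.85 at the undiluted d = 1.10. That beats the whole group at 53% drained (0.62) but not at 74% (0.88). Restriction gains only when the share ever drained is below about √0.533 = 0.73, which cannot be judged from the documents.

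**The case against.** Four objections have force.

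- **Group membership.** A reader might infer that the plan analyses every catheterised patient as drained. The clause in 2.1 can equally mean patients from whom CSF was released, and no passage settles it. Dilution is therefore conditional on one reading. The gap in the definition is not.
- **Snapshot.** A reader might infer that only about half the group would ever be drained. The 53% is a 24 h figure from another study with an assumed outcome mix. Section 2.4 does not confine release to 24 h, so the share ever drained may be higher and the loss smaller (power 0.97 at 90%).
- **Wrong target for the power argument.** A reader might infer that 0.99 would hold if every patient were drained, or that 0.62 or 0.88 should replace it. Neither follows. The 5.35 mmHg was never a treatment effect, and the endpoints are brain swelling and CPC, so 0.99 is unsupported for them even at 100% drained.
- **Estimand.** Comparing the whole strategy, with drainage on demand, is legitimate. Making the above-15 stratum the main basis for the conclusion, or matching exactly on ICP category, is a trade-off: it may lose power and matched pairs, and the distribution of immediate post-ROSC ICP is not given.

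All four stand, and they limit the point. They do not remove the undefined membership, the unlabelled estimand or the unqualified 0.99.

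**Conclusion.** The point holds in a limited form. Release depends on ICP, entry does not, and the plan's own figures imply that a material share of patients (33% to 74% by outcome group, about 53% at an even split) would be above the trigger at 24 h and the remainder not. If undrained catheterised patients are in the drainage group, the comparison estimates a drainage-on-demand strategy, and a null result says little about drainage itself.

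Separately, 0.99 is not a property of this design. Even as an ICP target, the drain-to-15 rule yields about 2.7 mmHg at an even split (power about 0.56) and 4.5 mmHg if all had poor outcome (about 0.94), against the 5.35 mmHg used.

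This rests on normality, equal groups, an assumed outcome mix and a fixed SD. The size of any dilution is unknown because the documents give no share ever drained. The finding concerns definition, labelling and stated power. It takes no position on the clinical threshold.

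**What to change.** **In 2.6:**
- Withdraw 0.99 as the power for the drainage comparison, or state that it applies only to the cited ICP contrast with every patient treated.
- Restate power at 62 patients for a drainage versus no-drainage difference in the primary endpoint, over a range of shares ever drained.

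**In 2.7:**
- State whether catheterised patients with no CSF released count in the drainage group.
- Keep the whole-group comparison, labelled as the effect of a drainage-on-demand strategy.
- Report the share that reached the trigger.
- Add a prespecified supporting estimate by immediate post-ROSC ICP (> 15 v ≤ 15 mmHg) in both groups. The plan already lists that reading for matching.

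Exact matching on ICP category is not required, nor is moving the main conclusion to the > 15 stratum.

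**Cost.** The change is SAP wording and one supporting model, with no new patients; the share reaching the trigger comes from ICP already monitored through the catheter. The stated power becomes less favourable, the supporting estimate will be imprecise, and patients who first cross 15 mmHg after the baseline reading fall outside its upper stratum.
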